**Title: The Diversity of Intestinal Microbiota in Patients With
Different Sedative-hypnotics and Mechanical Ventilation**

NCT number: 03401736

date of document: 2018/01/01

In order to study the relationship between biodiversity of intestinal microbiota in patients and different sedative-hypnotics undergoing mechanical ventilation. As propofol and sevoflurane are widely used in clinical anesthesia as sedative anesthetics, so we choose these two drugs as our observation objects.

Twenty patients undergoing cochlear implantation with endotracheal intubation in department of anesthesiology, shanghai ninth people's hospital, were allocated randomly to receive either propofol (n=10) or sevoflurane (n=10). The parameter settings of ventilator (Drager,Germany Zeus Infinity Empowered) were set as follows: tidal volume 10 ml / kg, frequency 22 times / min. Oxygen concentration was adjusted to maintain oxygen saturation no lower than 95%. The changes of hemodynamics were conventionally measured by the monitor. Propofol was used intravenously during the induction of general anesthesia (2.0mg / kg, 30 ~ 60s) in both groups. While in group propofol, continuous intravenous propofol maintenance ($7 \sim 9 \text{mg} \cdot \text{kg}^{-1} \cdot \text{h}^{-1}$) was used to achieve the stabilizing effect. And in group sevoflurane, inhalation (sevoflurane, 2.5-3.0 Vol%) maintenance was used. The BIS values of all the patients stay between 50 and 60. The average operation time was 5 hours. Faeces will be taken preoperative and postoperative so that the changes of the diversity of intestinal flora could be measured.

SPSS 21.0 software was used for data analysis. The measurement data from clinical studies are presented as means \pm SEM ($x \pm s$). The data between groups were subject to normal and variance homogeneity, independent sample t-test was used. Those who did not conform to normal distribution were tested by Wilcoxon rank sum test. The counting data were described by frequency and χ^2 test for groups comparison.

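### Does the unspecified timing of the stool samples leave the comparison of diversity change without a usable meaning?

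*Combined protocol and SAP*

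**What the plan says.** The combined protocol and SAP is a short document without numbered sections. Its opening paragraph gives the aim as studying "the relationship between biodiversity of intestinal microbiota in patients and different sedative-hypnotics undergoing mechanical ventilation".

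The methods paragraph randomises 20 patients, 10 to propofol and 10 to sevoflurane, and ends with the one sentence on sampling: "Faeces will be taken preoperative and postoperative so that the changes of the diversity of intestinal flora could be measured". The only other duration given for surgery is "The average operation time was 5 hours". It describes the length of the operation and does not time the sampling.

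The statistics paragraph compares groups as follows: "independent sample t-test was used" where normality and equal variance hold, and otherwise "Those who did not conform to normal distribution were tested by Wilcoxon rank sum test". Counts are compared with a chi-square test. None of these tests has a term for collection time.

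**The concern.** Change in diversity is the stated purpose of sampling, and a change is tied to the two moments at which it is measured. Here the moments are fixed only as before and after surgery. A stool passed soon after the operation and one passed days later both satisfy the rule. The document does not say which stool to use if a patient passes several, and it does not require the date and time to be written down.

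Three consequences seem to follow:

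- A reader could not tell from the plan what stage of recovery a difference, or the absence of one, refers to.
- If diversity moves during recovery, uneven timing adds noise to the change, and with 10 patients per arm there is little precision to spare.
- Time to the postoperative stool arises after randomisation, so allocation does not guarantee that it is alike in the two arms, and the planned tests would not reveal an imbalance.

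Times not noted at collection may also be impossible to recover later.

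**Working it through.** **What the text fixes and leaves open.** The plan states no sampling time, so there is no figure of its own to reproduce.

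| Element | In the document? |
|---|---|
| One sample before and one after surgery | Yes |
| Same rule in both arms | Yes; a single sentence covers all patients |
| Hours or days either side of surgery | No |
| Which stool counts | No |
| Collection time to be recorded | Not required, and not excluded |
| Evidence that timing varied or differed by arm | None |

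**Validity.** Treatment is randomised and the sampling rule does not depend on it. If the two drugs lead to different times of first stool, that difference is itself a consequence of assignment. The unadjusted comparison then estimates the total effect of assignment on the postoperative sample as collected. It does not separate a direct effect on the flora from an effect through timing, but the plan does not claim to do so. If timing varies in the same way in both arms, the type I error of the t-test is essentially unaffected: simulation with 200,000 trials per setting gave null rejection of 0.049 to 0.050.

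**Precision.** Only the 10 patients per arm come from the document. Everything else is assumed: a two-sided 5% t-test on change scores, normal timing noise with the same distribution in both arms, and noise of *s* in units of the SD from all other sources.

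- With 18 degrees of freedom (10 + 10 − 2), the noncentral t gives 80% power at a standardised effect of *d* = 1.325.
- Timing noise shrinks this to *d*/√(1 + *s*²). For example, at *s* = 0.5 it is 1.325/√1.25 = 1.185.
- If a tighter sampling rule halved *s* (also an assumption), the power in the fourth column would result.

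| *s* | Shrunken effect | Power | Power if *s* is halved | Gain, percentage points |
|---|---|---|---|---|
| 0.1 | 1.318 | 79.6% | 79.9% | 0.3 |
| 0.25 | 1.285 | 77.6% | 79.4% | 1.8 |
| 0.5 | 1.185 | 70.8% | 77.6% | 6.8 |
| 1.0 | 0.937 | 50.9% | 70.8% | 19.9 |

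The last row needs timing variance equal to all other variance combined. At a smaller effect of 0.5 SD, power is 18.5% with no timing noise, 17.7% at *s* = 0.25 and 15.7% at *s* = 0.5, so arm size is the main limit there.

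**What a stricter rule would change.** Suppose the rule were the last stool before induction and the first after surgery, with a target window and late samples kept in the main analysis. The lag from end of anaesthesia to sample would still vary between patients, because the patient determines when the first stool is passed. The last stool before induction can be identified only in retrospect. The main estimate would still mix times, though the times would be known. Excluding late samples would narrow the mix, but only by dropping patients on a post-randomisation event in a trial of 20.

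**The case for a change.** The strongest case for a change is about interpretation and does not depend on power. The plan does not define the time point of its main measurement. That holds whatever the true course of diversity over recovery, and it affects a null result as much as a positive one. Collection times cost a few form fields when the sample is taken and may be lost afterwards. A rule applied identically in both arms, with a lag table and no exclusions, would do no harm.

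Much of this stands. The stage of recovery is not prespecified, nothing suggests that extraction or redaction removed the text, and noting times is good practice. It does not follow that the result has no defined stage. If times were noted in the ordinary course, which the document does not exclude, the stage can be described when the results are reported.

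The remaining proposals do not correct an error. Choosing the first postoperative stool over a later one is a preference, since the document does not say which stage of recovery is of interest, and a window whose length is left to the sponsor settles little by itself. A lag-adjusted analysis would condition on a post-randomisation variable in 20 patients and could only be exploratory. The mixed tenses also leave it unclear whether enrolment had begun, so a window set beforehand may no longer have been possible.

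**Conclusion.** No change to the plan follows. The document leaves out a definition that a fuller protocol would give, and analysts can fill the gap sensibly by reporting the collection times they hold, the spread of lag and any missing samples by arm. That describes the data and alters neither the planned tests nor the conclusion drawn from them.

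The randomised before-and-after comparison stays valid as a total effect of assignment. Any bias or loss of precision cannot be established from the document. Under the assumed inputs, the power loss is 0.4 percentage points at timing noise of 0.1 SD (80.0 − 79.6) and 2.4 points at 0.25 SD (80.0 − 77.6). It becomes material only at 0.5 SD or more, a level that nothing in the document supports or rules out.

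This rests on two conditions: that the same sampling practice was applied in both arms, and that the result is read as describing the postoperative samples actually obtained and not a particular day of recovery. Evidence that staff collected samples on different schedules in the two arms would reopen the question; the document gives none.

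### The between-group tests do not adjust for preoperative diversity, and the plan does not say whether postoperative values or changes are tested

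*Combined protocol and SAP*

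**What the plan says.** In the Combined protocol and SAP, the unnumbered methods paragraph randomises 20 patients equally, 10 to propofol and 10 to sevoflurane. It gives the reason for the two stool collections: "Faeces will be taken preoperative and postoperative so that the changes of the diversity of intestinal flora could be measured".

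The unnumbered statistical analysis paragraph then lists the between-group tests. For continuous data: "The data between groups were subject to normal and variance homogeneity, independent sample t-test was used". Otherwise: "Those who did not conform to normal distribution were tested by Wilcoxon rank sum test". For categorical data: "The counting data were described by frequency and χ^2 test for groups comparison".

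That is the whole analysis plan. It names no diversity index and no covariate, and no ANCOVA, regression, paired or repeated-measures model. It does not say which quantity enters the t-test or the rank sum test. It also gives no significance level, effect size, SD or pre-post correlation.

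**The concern.** There are two linked gaps.

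- **Undefined analysis variable.** The t-test could be run on the postoperative value or on the pre-to-post change. The sampling sentence points towards change, but it explains why stool is collected and is not tied to either test.
- **No baseline adjustment.** A test on postoperative values ignores the preoperative sample. A test on change subtracts it in full, which over-corrects whenever the pre-post correlation is below 1. Neither adjusts for it.

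With 10 patients per arm, chance baseline imbalance is common. When it occurs, the two readings move the estimate in opposite directions, so the conclusion can turn on an unstated choice. The sample is fixed at 20, so any gain in precision has to come from the analysis, and the data needed for it are already being collected.

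**Working it through.** **Inputs from the plan:** n = 10 per arm; one preoperative and one postoperative sample; unadjusted t-test or rank sum test. The plan states no power or precision figure, so there is none to reproduce.

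**Assumptions (not in the plan):** two-sided 5% level; bivariate normal pre and post values with equal SD, set to 1; true difference 1.0 SD; pre-post correlation rho varied from 0 to 0.95.

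**Step 1: variance factors relative to the postoperative-only comparison.**
- Postoperative only: 1
- Change: 2(1 − rho)
- ANCOVA: (1 − rho²) × (1 + 1/(2n − 4)) = (1 − rho²) × 1.0625. The last term allows for chance imbalance in the covariate.

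ANCOVA equals postoperative-only at rho = √(1 − 1/1.0625) = 0.243, and equals change at rho = 2/1.0625 − 1 = 0.882. Between those values it is the most precise of the three. Outside them it is slightly less precise than one of the others.

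**Step 2: power.** Noncentrality is 1/√(V × 2/10), where V is the variance factor, with 18 df (17 for ANCOVA).
- Postoperative only: 1/√0.2 = 2.236, power 56.2%.
- Change at rho 0.7: V = 0.6, 1/√0.12 = 2.887, power 77.9%.
- ANCOVA at rho 0.7: V = 0.51 × 1.0625 = 0.542, noncentrality 3.04, power 81.7%.

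Simulation of 100,000 trials per scenario agrees (each cell: postoperative / change / ANCOVA):

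| rho | Power, % | Mean 95% CI half-width, SD |
|---|---|---|
| 0 | 56 / 32 / 54 | 0.93 / 1.31 / 0.96 |
| 0.3 | 56 / 43 / 58 | – |
| 0.5 | 56 / 56 / 66 | 0.93 / 0.93 / 0.83 |
| 0.7 | 56 / 78 / 82 | 0.93 / 0.72 / 0.68 |
| 0.8 | 56 / 92 / 92 | – |
| 0.9 | 56 / >99 / >99 | 0.93 / 0.41 / 0.42 |

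With no true difference, overall size is 5% for all three.

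**Step 3: chance imbalance.** The baseline difference between arms has SD √(2/10) = 0.447. P(gap above 0.5 SD in either direction) = 2 × (1 − Φ(0.5/0.447)) = 0.264.

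Given a gap of +0.5 SD, the postoperative estimate shifts by 0.5 × rho and the change estimate by −0.5 × (1 − rho). ANCOVA does not shift.
- rho 0.5: +0.25 / −0.25 / 0.00 SD
- rho 0.7: +0.35 / −0.15 / 0.00 SD

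Among the 26% of trials with a gap above 0.5 SD, the false-positive rate is 9.6/9.2/5.0% at rho 0.5 and 13.4/7.8/4.9% at rho 0.7. At rho 0.5 the first two are equal in theory, so their difference is simulation noise.

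**Step 4: cost of the open choice.** In 20,000 simulated trials per setting with a 1.0 SD difference, the probability that at least one of the two unadjusted tests is significant is 0.658, 0.733, 0.860 and 0.998 at rho 0.3, 0.5, 0.7 and 0.9. The two tests disagree with probability 2 × P(either) − P(post) − P(change):
- rho 0.3: 1.316 − 0.562 − 0.435 = 0.319
- rho 0.5: 1.466 − 0.563 − 0.566 = 0.337
- rho 0.7: 1.720 − 0.562 − 0.782 = 0.376
- rho 0.9: 1.996 − 0.561 − 0.997 = 0.438

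With no true difference, taking whichever test is significant gives 9.0% to 9.7% error over the same range, instead of 5%.

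**Step 5: skewed data.** Lognormal values, 40,000 trials per scenario, shift of 1.0 SD on the log scale. Power for rank sum on post / rank sum on change / ANCOVA on ranks is 51/33/52% at rho 0, 52/54/62% at 0.5 and 51/73/76% at 0.7. Size of ANCOVA on ranks is 5.1–5.3%.

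**The case against.** The strongest reply is that change is the only diversity quantity the plan names, so the postoperative-only reading, which has the lowest power at high rho, deserves less weight. If change is meant and rho is high, ANCOVA adds little: 78 against 82% at rho 0.7, virtually nothing at 0.8, and marginally less precision above about 0.88. A prespecified unadjusted comparison in a randomised trial is legitimate. The conditional false-positive rates describe a selected 26% of trials and are offset by lower rates in the rest.

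All of this is correct, and it limits the point to efficiency and specification. It does not remove it. The sampling sentence does not define the test variable. Even under the change reading, ANCOVA gains 10 points at rho 0.5 and 22 at rho 0, and the plan gives no basis for assuming that rho is high.

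Three smaller objections also stand in part:
- The exact rank sum test is slightly conservative here (size about 4.2–4.5%), so part of the rank-ANCOVA advantage is discreteness.
- A normality-triggered switch is not ideal with 20 patients, although a check of the two-stage procedure gave a size of 5.1–5.8%.
- ANCOVA presumes one number per patient. A between-sample composition measure would need its own method.

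**Conclusion.** The concern holds and should be acted on, but it does not invalidate the trial. The plan leaves the analysed variable undefined and does not adjust for a baseline it already collects. Among the three analyses ANCOVA is the safe choice when rho is unknown. At a 1.0 SD difference its largest shortfall is under 3 power points, whereas testing change can cost 24 points (32 against 56% at rho 0) and testing postoperative values alone can cost more than 40 (56 against over 99% at rho 0.9).

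These sizes rest on the assumed 5% level, equal SDs, 1.0 SD effect and range of rho. The absence of any covariate and of a defined test variable rests on the text alone. Confidence in the practical size of the gain is medium, because it depends on rho.

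**What to change.** Put into the statistical analysis paragraph:

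> Postoperative diversity ([one index, named in advance]) is compared between groups by ANCOVA with the preoperative value of the same index as covariate, reporting the adjusted difference with 95% CI. If the normality assumption fails for the model residuals (test and threshold named in advance), the same model is fitted to ranks.

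Add that any pre/post comparison within an arm, if made, must be paired. State also that an estimate from the rank model is in rank units, not diversity units.

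The cost is two sentences and one residual degree of freedom, with no extra patients or samples. If rho is near zero, the loss against a postoperative-only test is about 2 power points (54 against 56%). If the sponsor prefers to keep an unadjusted test, the plan should at least name the index and say whether the postoperative value or the change is tested. That closes the open choice but forgoes the gain in precision.

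### With 10 patients per arm, does planning a chi-square test for count data make its p-values unreliable?

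*Combined protocol and SAP*

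**What the plan says.** The combined protocol and SAP has no numbered sections. Its methods paragraph sets the sample: twenty patients "were allocated randomly to receive either propofol (n=10) or sevoflurane (n=10"). Its closing statistical paragraph deals with categorical data in one sentence: "The counting data were described by frequency and χ^2 test for groups comparison". It does not say whether the chi-square is Pearson's uncorrected statistic or the Yates version, and it gives no rule for small expected counts. It also states no significance level.

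Measurement data get a t-test with a fallback: "Those who did not conform to normal distribution were tested by Wilcoxon rank sum test". The outcome described is a change in diversity: "Faeces will be taken preoperative and postoperative so that the changes of the diversity of intestinal flora could be measured". No categorical endpoint is named anywhere.

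**The concern.** The usual textbook condition for the chi-square approximation is that every expected count is at least 5. With 10 per arm this fails at every margin but one. The plan offers a fallback when measurement data are not normal but none when counts are small, so the omission looks like an oversight.

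There are also concrete tables that seem to show harm. With 4/10 against 0/10, Pearson's test gives p = 0.025 and Fisher's gives p = 0.087. If the first figure were simply wrong, a study of 20 patients could report group differences that its data do not support. The natural remedy would be Fisher's test, at the price of one clause.

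**Working it through.** **Inputs.** Arms of 10 and 10, from the methods paragraph. Chi-square test, from the statistical paragraph. Two-sided alpha of 0.05 is an assumption. The plan has no sample-size or error-rate figure to reproduce.

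**1. The expected-count rule.** If m of the 20 patients are in the category, the expected counts are m/2 and (20 − m)/2 in each arm. Both reach 5 only if m ≥ 10 and m ≤ 10, so only at m = 10: one of the 19 non-degenerate margins. This part of the concern is right.

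**2. Where Pearson and Fisher differ.** With a and b patients in the category, the uncorrected statistic is X² = 20·[a(10 − b) − b(10 − a)]² / [10·10·m·(20 − m)]. For 4 v 0: 20·40²/(100·4·16) = 5.0, so p = 0.025. Over all 11 × 11 = 121 tables, Pearson rejects in 46 and Fisher in 34. The 12 that differ are six patterns and their mirror images.

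| Table | Pearson | Fisher | Barnard and Boschloo |
|---|---|---|---|
| 4 v 0, 10 v 6 | 0.025 | 0.087 | about 0.042 |
| 6 v 1, 9 v 4 | 0.019 | 0.057 | about 0.023 |
| 7 v 2, 8 v 3 | 0.025 | 0.070 | about 0.041 |

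The last column settles the point about exact tests. Barnard's and Boschloo's tests are also exact, and both reject in all six patterns. Pearson's p-values are somewhat too small, but the 5% decision agrees with these tests. Only Fisher's test differs.

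**3. The true type I error.** For a common event rate p, sum Bin(a; 10, p)·Bin(b; 10, p) over the tables that the test rejects.

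| p | Pearson | Fisher |
|---|---|---|
| 0.1 | 0.009 | 0.001 |
| 0.2 | 0.030 | 0.008 |
| 0.3 | 0.037 | 0.012 |
| 0.4 | 0.040 | 0.013 |
| 0.5 (maximum) | 0.042 | 0.013 |

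Pearson never exceeds 0.05.

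**4. How this fits with the error rates given the margin.** Given m, Pearson's error rate is 0.0867 at m = 4 or 16, 0.0573 at 7 or 13 and 0.0698 at 9 or 11. It is 0.0325 at 5 or 15, 0.0108 at 6 or 14, 0.0198 at 8 or 12, 0.0230 at 10, and 0 elsewhere. Weighted by the chance of each m at p = 0.5:

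2 × (0.0046·0.0867 + 0.0148·0.0325 + 0.0370·0.0108 + 0.0739·0.0573 + 0.1201·0.0198 + 0.1602·0.0698) + 0.1762·0.0230 = 2 × 0.0191 + 0.0041 = 0.042.

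The margins above 5% are offset by those below. The design fixes the arm sizes but not m, so this average is the error rate of the test as planned.

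**5. What Fisher's test would cost.** Power for 10% v 60% is 0.66 with Pearson and 0.47 with Fisher. For 20% v 70% it is 0.62 and 0.43. That is a loss of about 18 to 20 percentage points.

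**6. Which chi-square.** The Yates version rejects in 34 tables, the same 34 as Fisher. If that version is meant, the two tests make identical 5% decisions.

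**The case for a change.** The best counter-argument is that the balance at 10 v 10 is fragile. If one patient's data are missing (9 v 10), the maximum true error of the uncorrected test rises to 6.5%; at 9 v 9 it is 5.7%. Two stool samples per patient are needed, so a loss is conceivable. These figures reproduce, but they rest on a loss that the plan does not state and on the least favourable event rate. The excess over 5% is then 0.7 to 1.5 percentage points. At a nominal 1% level the maximum at 10 v 10 is 1.3%, also slightly above nominal.

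A statistician who conditions on both margins can fairly prefer Fisher's test and will regard the 8.7%, 7.0% and 5.7% figures as the relevant ones. That is a defensible position, but it is a choice between methods and does not show that the planned one is invalid.

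It also stands that the plan leaves the chi-square version open, and that in 12 of 121 tables the 5% decision depends on it. Naming the version would be tidier. The gap touches no analysis that the plan identifies: diversity is covered by the t-test and rank sum sentences if analysed as measurement data, and the sentence on counts is a general provision.

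**Conclusion.** The concern does not hold. The expected-count rule is broken at 18 of 19 margins, but it is a cautious rule of thumb. A direct calculation shows that the uncorrected test keeps its true error at or below 4.2% at the stated 10 v 10 design. It is not true that exact tests in general contradict its 5% decisions: two of the three exact tests examined agree with it in all six disputed patterns. Fisher's test would hold the error at 1.3% for a substantial loss of power, a trade-off on which reasonable statisticians differ.

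This rests on a two-sided 5% level, on two-by-two tables and on complete data in both arms. Tables with more categories have smaller expected counts and were not checked. What is left is an unspecified small-count rule and chi-square version for variables that the plan does not name, and no stated endpoint is shown to depend on it.
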